BOOG	Dutch Breast Cancer Trialists'-Group
CCMO	Central Committee on Research Involving Human Subjects; in Dutch: Centrale Commissie Mensgebonden Onderzoek
CV	Curriculum Vitae
DMFS	Distant Metastases Free Survival
eCRF	Electronic Case Report Form
ER	Estrogen Receptor
EU	European Union
GCP	Good Clinical Practice
IC	Informed Consent
IKNL	Integraal Kankercentrum Nederland
LI	Local Investigator
LR	Local Recurrence
LRR	Local Recurrence Rate
METC	Medical research ethics committee (MREC); in Dutch: medisch ethische toetsing commissie (METC)
NBCA	NABON Breast Cancer Audit
NKR	Netherlands Cancer Registry; in Dutch: Nederlands Kanker Registratie
OS	Overall Survival
PI	Principal Investigator
QoL	Quality of Life
RCT	Randomized Controlled Trial
RT	Radiotherapy
Sponsor	The sponsor is the party that commissions the organisation or performance of the research, for example a pharmaceutical company, academic hospital, scientific organisation or investigator. A party that provides funding for a study but does not commission it is not regarded as the sponsor, but referred to as a subsidising party.
TOP	Tailored treatment in Older Patients

WMO **Medical Research Involving Human Subjects Act (in Dutch: Wet Medisch-wetenschappelijk Onderzoek met Mensen)**

SUMMARY

Rationale: Breast cancer is the most common cancer type in women of 70 years and older, accounting for over 4.000 patients per year in the Netherlands(1). The benefit of standard adjuvant treatments in older patients with breast cancer are limited and influenced by both patient related factors as well as tumor related factors(2). Preventing over-treatment is therefore pivotal for these patients, allowing reduced treatment burden, improved quality of life and cost efficacy(2, 3). However, in clinical practice, older women are mostly treated according to general standards, not taking into account age specific factors(4). The Dutch TOP consortium (Tailored treatment in Older Patients) aims at tailoring treatment of older women with breast cancer by allocating treatment to those patients who will benefit and to prevent overtreatment in all others.

Previous studies, including the recent PRIME-II study, showed that omitting radiotherapy after breast conserving surgery in older patients is safe and does not result in decreased survival(5-7). Despite these results, currently, 98% of older patients with low risk breast cancer (obviating the need for adjuvant systemic therapy) in the Netherlands, still receive adjuvant radiotherapy after breast conserving surgery(8).

Objective: The main focus of the present trial is a first step towards treatment de-escalation in older breast cancer patients. For this, we initiate the first TOP consortium study (TOP-1).

Primary aim: to assess whether radiotherapy can be safely omitted after breast conserving surgery in elderly patients with a very low risk of local recurrence.

Secondary aim: assessment of: quality of life, toxicity, geriatric assessment, overall- and breast cancer specific survival, distant metastasis free survival, relating biomarkers to outcome (tumor characteristics, at least: IHC ER, PR, HER2 and Ki-67), additional state of the art molecular analysis if possible, development and validation of local recurrence rate prediction models, (cost) efficacy (comparison with historical control group) and implementation of findings into standard care.

Study design: TOP-1 is a national, multicenter, non-randomized, single-arm, prospective cohort study.

Study population: 800 Patients ≥ 70 years of age, with estrogen receptor positive disease without axillary nodal involvement and without indication for adjuvant hormonal therapy.

Intervention: Omitting adjuvant radiotherapy.

Main study parameters/endpoints: The primary endpoint is the local recurrence rate (LRR) at 5 years. Secondary determinants are the distant metastases free survival (DMFS), breast cancer-specific survival (BCSS) and overall survival (OS), quality of life, side-effects, costs, cosmetic outcome, geriatric assessment and biomarkers.

Nature and extent of the burden and risks associated with participation, benefit and group relatedness: The immediate impact for 95% of the TOP-1 participants is to be spared intensive radiotherapy and subsequent risk of side effects (such as fatigue, possible lung and cardiac damage). The other 5% will develop a local recurrence, which would not have happened with standard radiotherapy (3-fold of this risk, from 2.5% to 7.5% at five years). The majority of these local recurrences can however effectively be treated with salvage surgery and previous studies showed that patient survival will likely not be affected(9, 10). This limited risk of local recurrence increase for this particular patient population was deemed acceptable following consultation with patient advocates.

All TOP studies will be performed in a nationwide, multidisciplinary consortium, in close collaboration with Dutch Breast Cancer Trialists' Group (BOOG) together with patient advocates. Due to the nationwide character of this study and the involvement of all stakeholders, the findings can be easily implemented into national guidelines as a standard treatment. Because of this study, tools can be developed to predict a local recurrence in absence of any adjuvant therapy (providing a globally unique opportunity). Altogether, this will contribute to optimal therapy for elderly patients with BC without excessive treatment or under treatment. Eventually, this strategy can potentially be implemented in all breast cancer patients in the future.

Keypoints: elderly breast cancer patients, low risk tumors, multicenter implementation study, omitting radiotherapy after breast conserving surgery, first study TOP consortium, BOOG .

1. INTRODUCTION AND RATIONALE

Breast cancer (BC) is the most common cancer type in women of 70 years and older, accounting for over 4.000 patients per year in the Netherlands(1). With ageing of the population and the increasing life expectancy, the incidence of BC will rapidly increase in the Netherlands for the coming decades(11). Older patients with BC differ from younger patients in many aspects. Older women are more likely to have BC with estrogen receptor (ER) expression and less likely to have HER-2 positive tumors(2, 12). In addition, with increasing age the number of comorbidities will increase as well: multimorbidity (having two or more comorbidities) is present in 65% of patients of 65 to 84 years(13). A previous study showed that in contrast to outcome in younger counterparts, survival of older patients with BC has not improved over the last decades(14).

There is a lack of evidence on treating older patients with (breast)cancer. Despite comprising more than 40% of newly diagnosed BC, older patients are rarely included in randomized trials(15, 16). De Glas et al. showed that only 2% of current breast cancer trials are focused on the elderly(17). Necessitated by lack of evidence for the older patients with BC, results of trials in younger patients are often extrapolated to the older patient population and age specific aspects of older women are not taken into consideration(18, 19). In response to this current critical need the American Society of Clinical Oncology (ASCO) recently gave several recommendations on improving the evidence for treating older patients with cancer.(20)

Obviously overall survival deteriorates with increasing age among unselected older BC patients(21). Analysis of the TEAM study pointed out this was for a great part due to competing risk of mortality. We know that the benefit of standard adjuvant treatments in older patients with BC is therefore limited by both patient related factors (e.g. more co-morbidity) as well as tumor related factors (e.g. more often hormone receptor positive disease)(2). Preventing overtreatment is therefore pivotal for these patients, allowing reduced treatment burden, improved quality of life (QoL) and cost efficacy(2, 3).

However, among postmenopausal women with hormone receptor-positive BC, increasing age was also associated with a higher disease-specific mortality(22). This leads to both *overtreatment* as *undertreatment* of older patients with BC. Therefore, the Dutch **TOP** (Tailored treatment in **O**lder **P**atient) consortium has been established. The TOP consortium aims at tailoring treatment for older women with BC. This national consortium will provide the evidence needed for such change in practice, by initiating a series of multicenter national studies in women 70 years or older.

Adjuvant radiation therapy (RT) is one of the essential modalities in BC treatment. Previous studies, including the recent PRIME-II study, showed that omitting radiotherapy (RT) after breast conserving surgery (BCS) in older patients is safe and does not result in decreased survival(5-7). Despite these results, currently, 98% of older patients with low risk BC (obviating the need for adjuvant systemic therapy) in the Netherlands, still receive adjuvant RT after BCS(8). Therefore, the aim of TOP-1 study is to change this in clinical practice. This first TOP consortium study aims to assess whether RT can be safely omitted after BCS in patients ≥ 70 years of age, with ultra low risk, ER-positive disease without axillary nodal involvement, who would otherwise receive RT (and without indication for adjuvant systemic treatment). These patients will *not* receive adjuvant RT in the TOP-1 study, which may be regarded as the new standard. By improved tailoring, treatment burden (toxicity, hospital visits) will probably be reduced in clinical practice, QoL and presumably cost efficacy may improve. Extensive biomarker- and geriatric assessment studies will accompany all TOP studies.

The current trial therefore focuses on reducing overtreatment of BC, taking into consideration age and clinicopathological factors. This TOP-1 study is performed in close collaboration with patient advocates, as well as the Dutch Breast Cancer Trialists' Group (BOOG). This study is embedded in a nationwide, multidisciplinary consortium, which will allow rapid implementation of findings into national guidelines and standard treatment.

2. OBJECTIVES

[figure not shown]
Primary Objective: To determine if radiotherapy (RT) can safely be omitted after breast conserving surgery (BCS) in elderly patients at low risk of developing a local recurrence (LR)

Secondary Objectives:

1. To determine the DMFS, BCSS, and OS rates in this study population.
2. To determine the QoL of patients after they received treatment regarded as new standard practice, directly after BCS and at 12, 24, 36, 48 and 60 months after BCS.
3. To determine the geriatric status of the study population.
4. To determine the cosmetic outcome of the study population.
5. To determine if omitting RT after BCS in elderly patients with a low local recurrence rate (LRR) is cost efficacious.
6. To determine if poor outcome of the study population can be predicted at diagnosis by clinicopathological factors including IHC, ER, PR, HER2 and Ki-67 and emerging omics technology.

3. STUDY DESIGN

TOP-1 is a multicenter, prospective cohort study, in which all patients do not receive RT. The convincing evidence from RCT's support this nationwide implementation study in a low-risk population. The non-randomized design will enhance the participation rate and thereby the generalizability compared to an RCT. Furthermore, the primary focus is to determine whether the absolute LRR during a treatment regimen without RT is acceptable by itself in a representative cohort of older BC patients. The schematic design is given below.

Furthermore, the primary focus is to determine whether the absolute LRR during a treatment regimen without RT is acceptable by itself in a representative cohort of older BC patients. In contrast to the previous mentioned studies (CALBG 9343 trial, PRIME II), this study is an observational cohort with the focus on implementation in clinical practice, showing the uniqueness of this study.

The TOP-1 study is conducted in collaboration with the BOOG. The supervision of TOP-1 will be performed by PI's and the LUMC Datacenter.

4. STUDY POPULATION

4.1 Population (base)

The TOP-1 study will be conducted in collaboration with the BOOG. All hospitals in the Netherlands have shown interest in the concept of TOP. We expect therefore to accrue patients from most Dutch hospitals. After a kick-off meeting all patients that meet the inclusion criteria and consent to participate will be treated according to the TOP-1 study. An enrolment log will be used to keep track of patients that receive RT despite this implementation study.

The duration of the TOP-1 study is estimated to consist of 48 months recruitment with a minimum of 60 months of follow-up.

In view of the fact that 338 TOP-1 eligible patients are treated with BCS yearly in The Netherlands, and a further 133 patients with ablative surgery, possibly to avoid RT (for a total of n=471/year; NCR data 2008-2012), it should be feasible to include this number of patients within the time span of 48 months.

4.2 Inclusion criteria

In order to be eligible to participate in this study, a patient must meet all of the following criteria:

- age 70 years or older;
- within 3 months after BCS;
- tumor \varnothing <1 cm grade 1-2 or tumor \varnothing 1-2cm grade 1;
- tumor ER>50% positive, HER2 negative;
- sN0 or sN0(itc);
- R0 resection;
- Female.

4.3 Exclusion criteria

A potential subject who meets any of the following criteria will be excluded from participation in this study:

- Indication for hormonal therapy;
- Bilateral.

In case of a multifocal tumour: only the diameter of the largest lesion counts.

TNM Classification according to AJCC Cancer Staging Manual 7th edition (2010).

4.4 Sample size calculation

Data of the Netherlands Cancer Registry (NKR) of 2003-2008 showed a LRR of 1.3% after 5 years following RT in patients representative for those eligible for the TOP-1 study, with a 99% CI of 0.6-2.5%. A 5 years LRR greater than 2.5% after RT can therefore be excluded in this group of patients. This worse-case LRR risk of 2.5% at 5-years in current practice was used to determine the necessary sample size for TOP-1. Omitting RT will triple the risk of LRR, thus from 2.5% to 7.5%. In close collaboration with Dutch Breast Cancer Trialists' Group (BOOG) and together with patient advocates, it was concluded that a 5-years LRR risk of 10% or more would be unacceptable in this patient population. A sample size of 800 patients is required to achieve a power of >80% to exclude a LRR at 5 years of 10% or more, if the actual 5-year LRR risk is 7.5% (at a one-side alpha of 0.05 and taking into account competing risks of death). The actual power will likely be higher as the actual LRR risk without RT will probably be lower (considering above data of NKR and previous RCT's like the PRIME-II study and CALBG-study which resulted considerably lower risk of LRR).

This conservative approach was chosen so that:

- 1) the study still has enough power to conclude that omitting RT is acceptable in this patient group, even if the 5-year risk of LRR is unexpectedly high (i.e. 7.5%).
- 2) that with the most likely LRR risk increase (i.e. from 1.3% in current practice to 3.9% in TOP-1), we will be able to exclude a 5-year LRR risk of even less than the acceptability boundary of 10% following omission of RT, which will improve implementation;
- 3) that LRR risk estimations are sufficiently precise and the number of LR will be enough to answer secondary research questions in a meaningful way (i.e. costs efficacy and developing and validating risk models for LRR);
- 4) also with even lower LR risk numbers than currently anticipated, this study design will prove that LR risk is increased in the predefined acceptable range (omitting RT is considered to be acceptable if an absolute 5-year LRR risk exceeding 10% can be ruled out).

5. METHODS

5.1 Study parameters/endpoints

5.1.1 Main study parameter/endpoint

LRR at 5 years

5.1.2 Secondary study parameters/endpoints

LRR at 10 years

DMFS, BCSS and OS at 5 years and 10 years

QoL

Side-effects

Costs

Cosmetic outcome

Geriatric assessment

Biomarkers

5.2 Registration procedure

After having properly checked all eligibility criteria and having obtained patients informed consent by the local study team, patients will be registered online through the ProMISe program or by phone, fax or email at the LUMC Datacenter.

Online registration

Registration can be performed online 24 hours per day through the ProMISe registration program.

Go to:

www.clinicalresearch.nl/PROMISE/S/HEIT/S_O_LUMC_C_HEELK_TOP_/LOGON/INDEX.HEI

Investigators, datamanagers or research nurses can apply to the LUMC Datacenter for a username and password. E-mails with the answered questions and the patient number will be automatically sent to the local and central study team.

Registration by email, phone or fax

Registration can be done by email [contact], [contact]; Monday-Friday; 9:00-17:00 or [contact]. During the registration procedure eligibility criteria will be checked.

After registration, a sequential identification number will be assigned. This number has to be recorded on the registration form, along with the registration date. The registration form must be signed by the local investigator (in case of faxed registration, the confirmation of

the data manager/research nurse also has to be signed by the local investigator) and filed with the eCRFs. An automatic e-mail will be sent to the local and central study team (see online registration).

5.3 Study procedures

Current practice consists of adjuvant RT after BCS. The new standard practice will be no adjuvant RT after BCS. The primary endpoint (the LRR at 5 years) and the secondary endpoints: LRR at 10 years, DMFS, BCSS and OS will be determined according to standard clinical care by local datamanagers from Integraal Kankercentrum Nederland (IKNL). An electronic case report form (eCRF) will be used to collect the necessary data. The treating health care provider can delegate the filling out the eCRF.

Baseline data will be derived from the NABON Breast Cancer Audit (NBCA) (see 5.7).

The other secondary endpoints will be determined by assessments. This data will be collected in the local hospital where patient is treated. After BCS, a geriatric assessment will be done. These assessments focus on the elderly and their mental- and physical status.

At 0, 12, 24, 36, 48 and 60 months after BCS patients will be followed up by collecting questionnaires. The 0 moment is defined as 0 days to 2 weeks after registration. This allows patient a considerable time to withdraw from the study and still receive the regular care (adjuvant radiotherapy) within 6 weeks after surgery. After informed consent is obtained by the health care provider, the patient will be asked if they would prefer to receive a link to the questionnaires provided by e-mail or receive the questionnaires by post. A stamped envelope will be provided to return the filled out questionnaires if patient's preference is to fill out the questionnaire in hardcopy. If patients do not complete the digital version of the questionnaire or do not return the hardcopy, patients will be contacted again by the local study team. The LUMC Datacenter will inform the local study team about the incomplete or missing questionnaire.

The geriatric assessment and the questionnaires used, correspond to those used in the CLIMB study. The aim of this ongoing prospective non-randomized longitudinal study is to gain knowledge on the prevalence and consequents of functional, cognitive, psychological and social restraints in elderly with breast cancer in comparison to elderly without breast cancer. The study population consists of 650 breast cancer patients of 70 years and older who underwent loco-regional treatment in different hospitals in the Leiden/The Hague area. These patients were treated according to guidelines, meaning patients that had

breast-conserving surgery will have been treated with radiotherapy. Including the same geriatric assessment and questionnaires in our study, allows us to compare our patients to patients that underwent radiotherapy as part of their loco-regional treatment.

The geriatric assessment and QoL will be assessed by the following instruments:

Just after the BCS the following assessments will take place in the hospital:

- Malnutrition Universal Screening Tool (MUST)
- Mini Mental State Examination
- Timed up and Go test

These questionnaires will be given to the patient at 0, 12, 24, 36, 48 and 60 months after BCS:

- Groningen Activiteiten Restrictie Schaal (GARS) questionnaire
- EORTC QLQ-C30 questionnaire
- EORTC QLQ-BR23 questionnaire
- Cantrils Ladder
- De Geriatric Depression Scale (GDS)
- Apathy scale of Starkstein (AS)
- Loneliness questionnaire of De Jong-Gierveld
- The Nurses' Health Study II Activity and Inactivity Questionnaire

Prior to using the geriatric assessment and questionnaires for the CLIMB study, a pilot study was performed to define the burden of the geriatric assessment and the questionnaires. In cooperation with the patient's advocacy group BVN, a handful of elderly breast cancer patients filled out the questionnaires. The burden deems acceptable according to the BVN.

Tumor tissue for future biomarker research

The tumour tissue is routinely stored by the pathologists. For future purposes we will ask patients informed consent to send this tumour tissue to the LUMC for biomarker research if a research question relates to this study.

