5.4 Withdrawal of individual subjects

Patients can leave the study at any time for any reason if they wish to do so without any consequences. The investigator can decide to withdraw a subject from the study for urgent medical reasons. Patients will not be contacted for filling out the questionnaires.

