7.2 Secondary study parameters

For the second endpoints, distant recurrence rates and BC specific survival will be calculated with the same methodology. QoL will be measured according to the methodology provided by several questionnaires and compared with the available mean scores of the general population. The change of QoL over time will be evaluated and specific aspects of QoL (e.g. fear and fatigue) will be taken into account as well. Geriatric status will be measured by a complete geriatric assessment.

In this unique study of primary BC patients that will only receive surgical treatment, we will validate and develop adverse outcome risk prediction models, according to state-of-the-art methodology suitable for small datasets. All these analyses will take the competing risk of death into account, and we will specifically focus on the (added) value of biomarkers to predict patient outcome.

By using our study data and data of previous studies, we will develop markov models to determine costs-efficacy of omission of adjuvant RT for quality adjusted life years gained from a societal perspective.

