7.3 Interim analysis

There are two reasons why interim analysis is not considered necessary or appropriate. Firstly, an interim analysis is not considered of value for the study population. We expect to have included most of the participants by the time an interim analysis could be performed. Delayed radiotherapy after breast conserving therapy is not considered effective. Therefore we cannot offer this treatment to this study population even when we find the local recurrence rate at 2,5 years higher than expected.

Secondly, this study is designed as an implementation study because there is enough evidence (see introduction/rationale) that it is safe to omit radiotherapy in this study population. This is also the reason for not involving a control group. By using this study design we can gain extra information on quality of life and create robust evidence for safely omitting radiotherapy. A local recurrence rate exceeding 10% after five years is not expected. If it does exceed this number, we cannot directly conclude it would be unsafe to omit radiotherapy because of the past research that has been done on this topic.

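### Entry is open until 3 months after surgery, but section 5.3 assures every registered woman that she can withdraw and still have radiotherapy within 6 weeks; after day 42 this cannot be true

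*Protocol*

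**What the plan says.** Three provisions of the protocol bear on this point.

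- **Entry window (section 4.2).** A woman may enter "within 3 months after BCS". Section 5.2 has the eligibility criteria checked before registration and again during it, so this limit governs the registration date.
- **Time to reconsider (section 5.3).** "The 0 moment is defined as 0 days to 2 weeks after registration". The next sentence says that this leaves the patient ample time to "withdraw from the study and still receive the regular care (adjuvant radiotherapy) within 6 weeks after surgery". It names no subgroup and sets no latest registration date.
- **Withdrawal (section 5.4).** "Patients can leave the study at any time for any reason". Nothing is said about radiotherapy afterwards. Section 5.5, on follow-up after withdrawal from treatment, is marked not applicable.

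No other section requires registration within 4 or 6 weeks of surgery, and none says what applies to women registered later.

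**The concern.** The time to reconsider runs from registration. The radiotherapy deadline runs from surgery. Nothing in the protocol ties the two together, and the entry window is about twice as long as the deadline. The assurance in 5.3 therefore cannot hold for every woman whom 4.2 admits.

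What is at stake is the accuracy of a statement about going back to standard care. The only intervention in this trial is leaving radiotherapy out, and 5.3 is the one place that describes how a woman who changes her mind gets it after all. On the protocol's own planning figures (section 8.3), her choice is between a 5-year local recurrence risk of 2.5% with radiotherapy and 7.5% without. A site that relies on 5.3 could give a late registrant an assurance that her dates already rule out.

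**Working it through.** This is calendar arithmetic, with day 0 as the day of surgery.

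**Inputs**

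- Radiotherapy limit, section 5.3: 6 weeks = 6 × 7 = day 42.
- Entry window, section 4.2: 3 months, taken as 91 days; 84, 90 and 92 days are also tried.
- Time to reconsider, section 5.3: 0 to 14 days from registration.

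**1. Registration after which the assurance must fail.** If the woman withdraws on the day she registers and radiotherapy could start at once, she must be registered by day 42. The permitted days after that are 91 − 42 = 49, and 49/91 = 54% of the window. For a woman registered on day 91, week 6 passed 49 days before she entered.

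**2. Registration that leaves the full 2 weeks.** The latest day is 42 − 14 = day 28. The permitted days after that are 91 − 28 = 63, and 63/91 = 69% of the window. Women registered on days 29 to 42 have some time to reconsider, but less than 2 weeks.

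**3. Sensitivity to the reading of 3 months**

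| Window (days) | After day 42 | After day 28 |
|---|---|---|
| 84 | 42 (50%) | 56 (67%) |
| 90 | 48 (53%) | 62 (69%) |
| 91 | 49 (54%) | 63 (69%) |
| 92 | 50 (54%) | 64 (70%) |

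No reading of 3 months removes the conflict.

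**4. Radiotherapy planning time.** Both limits above allow none. Any planning time moves them earlier day for day. The protocol gives no figure, so none is put in here.

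**The case against.** The best defence is that 5.3 describes the usual case. The sentence is an explanatory remark within the questionnaire schedule. It creates no procedure, and the 3-month criterion may be an outer bound that few women approach. That may well be how the trial runs, and it limits what can be said about scale. But the protocol does not say so; it states the assurance without qualification and accepts later entry.

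A second defence is that the two clocks may start on different days. Section 4.2 counts from breast conserving surgery, and 5.3 counts from surgery. As 4.2 also requires an R0 resection, a re-excision could make the last operation the later one. The protocol defines neither date this way. Even then it would help only women who had a re-excision, and for registration on day 91 the last operation would have to fall on day 49 or later (91 − 42).

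Third, 5.4 lets a woman leave whenever she likes, and what her clinician then offers is ordinary care. This is true, but leaving does not bring back a date that has passed.

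Fourth, a woman registered after day 42 had already missed week 6 before she enrolled, so registration did not take that option from her. This stands. For her the fault is that the statement is inaccurate, not that entry caused the delay.

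Fifth, the patient information may already deal with this. Those pages are not in this copy, so whether women are in fact misinformed cannot be judged. The sentence in 5.3 is wrong in either case.

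A reader might also go further and infer from 7.3, "Delayed radiotherapy after breast conserving therapy is not considered effective", that late registrants who withdraw have no useful treatment left. The text does not support that. The sentence explains why an interim look at 2.5 years would not help participants, a far longer delay than 7 to 13 weeks. The protocol does not say at what delay radiotherapy loses its value.

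**Conclusion.** The point holds in a limited form. Sections 4.2 and 5.3 cannot both be true for every participant. The 6-week assurance fails for any registration after day 42. It leaves the full 2 weeks only for registration by day 28, and that is before planning time. This rests on both clocks starting at the same operation and on the entry criterion being applied at registration, as 5.2 indicates.

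The 54% should not be read as a share of women. It is a share of permitted days, and the protocol gives no distribution of registration times; the number affected could be small. Nor does the conflict reach the main analysis: the sample size, the comparison of the upper confidence bound with 10%, and the 5-year local recurrence risk, which 7.1 times from registration, are untouched. It should be corrected because it misstates the one described route back to standard care, and correcting it costs almost nothing.

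**What to change.** Keep the 3-month entry window and make two changes.

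1. In 5.3, limit the 6-week statement to women registered early enough for the time to reconsider and the planning of radiotherapy to be finished by day 42. If the full 2 weeks is allowed, that means registration by day 28 at the latest, less the planning time. The clinical leads should set that planning time and write the resulting day into the protocol.
2. Require that women registered later be told, before they consent, that the 6-week limit cannot be met if they change their mind, and which radiotherapy option remains for them. Add this to the patient information if it is not already there.

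The cost is a change of wording and two rules for sites to apply. No new visits or data are needed: section 5.2 already records the registration date, and the surgery date is needed to check the 3-month criterion. Shortening the entry window to the same day would give a single rule, but the loss of accrual cannot be sized from the protocol, so changing the wording is the safer choice.
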